### **8.3.2.9. Antidrug Antibodies**

The occurrence of ADA formation will be assessed as outlined in Section [8.9](#).

### **8.3.2.10. Hepatobiliary Disorders**

All events of treatment-emergent biliary colic, cholecystitis, or other suspected events related to gallbladder disease should be evaluated and additional diagnostic tests performed, as needed. In cases of elevated liver markers, hepatic monitoring should be initiated as outlined in Section [8.2.5.1](#).

### **8.3.2.11. Severe Gastrointestinal Adverse Events**

Tirzepatide may cause severe GI AEs, such as nausea, vomiting, and diarrhea. Information about severe GI AEs as well as antiemetic/antidiarrheal use will be collected in the eCRF/AE form. For detailed information concerning the management of GI AEs, please refer to Section [6.6.2](#).

### **8.3.2.12. Acute Renal Events**

Renal safety will be assessed based on repeated renal function assessment, as well as assessment of AEs suggestive of acute or worsening of chronic renal failure. Gastrointestinal AEs have been reported with tirzepatide, including nausea, diarrhea, and vomiting. This is consistent with other GLP-1R agonists (Aroda and Ratner 2011). The events may lead to dehydration, which could cause a deterioration in renal function, including acute renal failure. Participants should be advised to notify investigators in case of severe nausea, frequent vomiting, or symptoms of dehydration.

### **8.3.2.13. Depression, Suicidal Ideation, or Behavior Monitoring**

Participants will be monitored for depression and suicidal ideation or behavior through AE collection and by using the C-SSRS and the PHQ-9. Participants will be referred to an MHP if in the opinion of the investigator it is necessary for the safety of the participant or if the participant had any of the following:

- a PHQ-9 score  $\geq 15$
- C-SSRS responses of
  - A “yes” answer to Question 4 (Active Suicidal Ideation with Some Intent to Act, Without Specific Plan) on the “Suicidal Ideation” portion of the C-SSRS
    - or
    - A “yes” answer to Question 5 (Active Suicidal Ideation with Specific Plan and Intent) on the “Suicidal Ideation” portion of the C-SSRS
      - or

- A “yes” answer to any of the suicide-related behaviors (actual attempt, interrupted attempt, aborted attempt, preparatory act, or behavior) on the “Suicidal Behavior” portion of the C-SSRS

## **8.4. Treatment of Overdose**

Study drug overdose (more than the specified number of injections) will be reported as an AE. In the event of an overdose, refer to the IB for tirzepatide.

## **8.5. Pharmacokinetics**

Not applicable.

## **8.6. Pharmacodynamics**

Samples to assess the PD properties of tirzepatide are included in the efficacy measures and not applicable in this section.

## **8.7. Genetics**

A whole blood sample will be collected for pharmacogenetic analysis as specified in the SoA (Section 1.3) where local regulations allow.

Samples will not be used to conduct unspecified disease or population genetic research either now or in the future. Samples will be used to investigate variable response to tirzepatide and to investigate genetic variants thought to play a role in obesity. Assessment of variable response may include evaluation of AEs or differences in efficacy.

All samples will be coded with the participant number. These samples and any data generated can be linked back to the participant only by the investigator site personnel.

Samples will be retained at a facility selected by Lilly or its designee for a maximum of 15 years after the last participant visit for the study, or for a shorter period if local regulations and/or Ethical Review Boards (ERBs)/Institutional Review Boards (IRBs) impose shorter time limits. This retention period enables use of new technologies, response to regulatory questions, and investigation of variable response that may not be observed until later in the development of tirzepatide or after tirzepatide becomes commercially available.

Molecular technologies are expected to improve during the 15-year storage period and, therefore, cannot be specifically named. However, existing approaches include whole genome or exome sequencing, genome wide association studies, and candidate gene studies. Regardless of technology utilized, genotyping data generated will be used only for the specific research scope described in this section.

## **8.8. Biomarkers**

Biomarker research is performed to address questions of relevance to drug disposition, target engagement, PD, mechanism of action, variability of participant response (including safety), and clinical outcome. Sample collection is incorporated into clinical studies to enable examination of these questions through measurement of biomolecules including DNA, proteins, lipids, and other cellular elements.

Serum and plasma samples for biomarker research (nonpharmacogenetic stored samples) will be collected at the times specified in the SoA (Section 1.3) where local regulations allow.

Samples will be used for research on the drug target, disease process, variable response to tirzepatide, pathways associated with obesity, mechanism of action of tirzepatide, and/or research method or in validating diagnostic tools or assay(s) related to obesity.

All samples will be coded with the participant number. These samples and any data generated can be linked back to the participant only by the investigator site personnel.

Samples will be retained at a facility selected by Lilly or its designee for a maximum 15 years after the last participant visit for the study, or for a shorter period if local regulations and ERBs impose shorter time limits. This retention period enables use of new technologies, response to regulatory questions, and investigation of variable response that may not be observed until later in the development of tirzepatide or after tirzepatide becomes commercially available.

## 8.9. Immunogenicity Assessments

Where local regulations and ERBs allow, blood samples for immunogenicity testing will be collected to determine antibody production against tirzepatide as specified in the SoA (Section 1.3).

For immunogenicity testing, venous blood samples will be collected from each participant according to the SoA (Section 1.3) to determine antibody production against tirzepatide. To interpret the results of immunogenicity, a venous blood sample will be collected at the same time points to determine the plasma concentrations of tirzepatide. All samples for immunogenicity should be taken predose when applicable and possible.

In the event of systemic drug hypersensitivity reactions (immediate or nonimmediate), additional unscheduled samples should be collected as detailed in Section 8.3.2.7 (Hypersensitivity Reactions). Instructions for the collection and handling of blood samples will be provided by the sponsor. The actual date and time (24-hour clock time) of each sampling will be recorded. Samples collected at Visit 801 will assess immunogenicity at washout of tirzepatide (5 half-lives post end of treatment).

Immunogenicity will be assessed by a validated assay designed to detect ADAs in the presence of tirzepatide at a laboratory approved by the sponsor. Antibodies may be further characterized for their ability to neutralize the activity of tirzepatide on GIPR and GLP-1R. Positive tirzepatide ADA samples will be tested for cross-reactivity with native GIP and GLP-1, and, if positive, may then be tested for neutralizing antibodies against native GIP and/or GLP-1. In vivo laboratory indicators for effect on weight loss and PK will be utilized to detect potential neutralizing effect of ADAs against tirzepatide.

Treatment-emergent ADAs are defined in Section 9.4.5.

Samples will be retained for a maximum of 15 years after the last participant visit, or for a shorter period if local regulations and ERBs allow, at a facility selected by the sponsor. The duration allows the sponsor to respond to future regulatory requests related to tirzepatide. Any samples remaining after 15 years will be destroyed.

Concentrations of tirzepatide will be assayed using a validated liquid chromatography mass spectrometry method. Bioanalytical samples collected to measure tirzepatide concentrations will be retained for a maximum of 1 year following last subject visit for the study. During this time, samples remaining after the bioanalyses may be used for exploratory analyses such as metabolism work, protein binding, and/or bioanalytical method cross-validation.

## **8.10. Health Economics**

Health Economics parameters are not evaluated in this study.

## 9. Statistical Considerations

### 9.1. Statistical Hypotheses

The alternative hypothesis for the primary objective is the following:

H1: QW tirzepatide MTD is superior to placebo for percent change from randomization (Week 36) in body weight at 88 weeks.

The alternative hypotheses for the key secondary objectives controlling for Type 1 error rate are the following:

H2: QW tirzepatide MTD is superior to placebo for change from randomization (Week 36) in body weight (kg) at 88 weeks.

H3: QW tirzepatide MTD is superior to placebo for change from randomization (Week 36) in waist circumference (cm) at 88 weeks.

H4: QW tirzepatide MTD is superior to placebo for percentage of participants who maintain  $\geq 80\%$  of the body weight lost during the open-label lead-in period at 88 weeks.

H5: QW tirzepatide MTD is superior to placebo for delaying the onset of returning to  $>95\%$  body weight at baseline (Week 0) during the double-blind treatment period.

H6: QW tirzepatide MTD is superior to placebo for percentage of participants who achieve  $\geq 5\%$  body weight reduction from Visit 2 (Week 0) at 88 weeks.

H7: QW tirzepatide MTD is superior to placebo for percentage of participants who achieve  $\geq 10\%$  body weight reduction from Visit 2 (Week 0) at 88 weeks.

H8: QW tirzepatide MTD is superior to placebo for percent change from randomization (Week 36) in body weight at 64 weeks.

### 9.2. Sample Size Determination

Approximately 1000 participants will be screened and 750 participants enrolled into the 36-week open-label tirzepatide lead-in treatment period in order to get approximately 600 participants to be randomized in a 1:1 ratio to tirzepatide MTD (300 participants) or placebo (300 participants).

The sample size determination assumes that evaluation of superiority of tirzepatide MTD to placebo will be conducted at a 2-sided significance level of 0.05 using a 2-sample t-test.

Additionally, a difference of at least 6% mean body weight percentage change from randomization (36 weeks) to 88 weeks between tirzepatide MTD and placebo, a common SD of 8%, and a dropout rate of 25% are assumed for statistical power calculations. Under the assumptions above, randomizing 600 participants in a 1:1 ratio to tirzepatide MTD (300 participants) and placebo (300 participants) provides more than 90% power to demonstrate superiority of tirzepatide MTD to placebo.

### 9.3. Populations for Analyses

For purposes of analysis, the following populations are defined:

Population	Description
Entered	All participants who sign informed consent
Enrolled	All participants who are assigned to open-label tirzepatide treatment
Randomized	All participants who are randomly assigned a study treatment (double-blind)
Modified Intent-to-Treat (mITT)	All enrolled participants who are exposed to at least 1 dose of study drug.
Efficacy Analysis Set (EAS)	Data obtained during the double-blind treatment period from the mITT population, excluding data after discontinuation of study drug (last dose date + 7 days).
Full Analysis Set (FAS)	Data obtained during the double-blind treatment period from the mITT population, regardless of adherence to study drug.
Safety Analysis Set (SS)	Data obtained during the double-blind period and safety follow-up period from the mITT population, regardless of adherence to study drug.

### 9.4. Statistical Analyses

#### 9.4.1. General Considerations

Statistical analysis of this study will be the responsibility of the sponsor or its designee. Any change to the data analysis methods described in the protocol will require an amendment only if it changes a principal feature of the protocol. Any other change to the data analysis methods described in the protocol, and the justification for making the change, will be described in the statistical analysis plan (SAP) and the clinical study report (CSR). Additional exploratory analyses of the data will be conducted as deemed appropriate.

Unless otherwise noted, all tests of treatment effects will be conducted at a 2-sided alpha level of 0.05, and all confidence intervals will be given at a 2-sided 95% level. In statistical summaries and analyses, data will be analyzed as randomized.

Unless specified otherwise, efficacy analyses will be conducted using the efficacy analysis set (EAS), and safety analyses will be conducted using the safety analysis set (SS).

Unless specified otherwise, for analyses in the double-blind treatment period, baseline is defined as the last nonmissing data collected prior to or at randomization (Week 36); for analyses in the lead-in period, baseline is defined as the last nonmissing data collected prior to or at study entry (Week 0).

Summary statistics for continuous measures will include sample size, mean, SD, median, minimum, and maximum. The analysis model to make comparisons among treatment arms relative to continuous measurements assessed over time will be a mixed-model for repeated measures (MMRM) with terms of treatment, visit, treatment-by-visit interaction, stratification factors, and baseline measurement as a covariate. An unstructured covariance structure will model the relationship of within-patient errors.

The Kaplan-Meier method will be used for estimation of cumulative event-free survival rates over time, and Cox proportional hazards regression analysis will be used to compare hazard rates among treatments.

Summary statistics for categorical measures (including categorized continuous measures) will include sample size, frequency, and percentages. Logistic regression will be used to examine the treatment difference in binary efficacy outcomes if there is a need to adjust for covariates. Otherwise, Fisher's exact test will be used to examine the treatment difference in categorical outcomes.

Summary statistics for discrete count measures will include sample size, mean, SD, median, minimum, and maximum. The negative binomial regression model will be used for the treatment comparison of discrete count measures.

Other statistical methods may be used, as appropriate, and details will be described in the SAP.

#### **9.4.2. Treatment Group Comparability**

##### **9.4.2.1. Participant Disposition**

A detailed description of participant disposition will be provided at the end of the study.

Frequency counts and percentages of all participants screened, enrolled, and randomized will be summarized.

Frequency counts and percentages of participants who completed the study and those who prematurely discontinued the study (and/or study drug), including reason for premature discontinuation, will be summarized for both the open-label lead-in period and the double-blind period.

A Kaplan-Meier analysis of time from randomization to premature discontinuation from study and/or study treatment during the double-blind period by treatment group will be provided.

##### **9.4.2.2. Participant Characteristics**

Demographics will be summarized for all enrolled participants.

Demographics will also be summarized by treatment group for all randomized participants.

##### **9.4.2.3. Concomitant Therapy**

Concomitant medications during the double-blind treatment period will be summarized by treatment group for all randomized participants.

Concomitant medications during the open-label lead-in treatment period may also be summarized for all enrolled participants.

##### **9.4.2.4. Treatment Compliance**

Frequency counts and percentages of participants compliant to study drug will be summarized for both the open-label lead-in period and double-blind period.

#### **9.4.3. Efficacy Analyses**

##### **9.4.3.1. Primary Analyses**

There will be 2 estimands of interest in comparing efficacy of tirzepatide MTD with placebo.

For the FDA, the primary efficacy analysis will be guided by the “hybrid” estimand and will be conducted using the full analysis set (FAS). This assessment will analyze percent change in body weight from randomization (Week 36) to the 88-week visit using an analysis of covariance (ANCOVA). The model will include terms of treatment, stratification factors, and baseline body weight as a covariate. Missing data solely due to a pandemic or natural disaster (after other reasons for missing data are ruled out) will be considered missing at random, and missing data will be imputed using all nonmissing data of the primary outcome from the same treatment arm. Missing data of the primary outcome measurement due to all other Intercurrent Events will be imputed based on retrieved dropouts in the same treatment arm, defined as observed primary outcome measurements from participants in the same treatment group who had their efficacy assessed after early discontinuation of study drug. In cases where there are not enough retrieved dropouts to provide a reliable imputation model (for example, the model implemented by the SAS program does not converge), an alternative multiple imputation method with reference to the placebo group (that is, placebo multiple imputation) will be used. Analysis will be conducted with multiple imputations.

For all other purposes, the primary efficacy analysis will be guided by the “efficacy” estimand, which reflects efficacy prior to discontinuation of study drug and is conducted using the EAS. The primary analysis model will be an MMRM for body weight percent change over time. The response variable of MMRM will be the percent change in body weight from randomization obtained at each scheduled postbaseline visit. The independent variables are treatment group (tirzepatide MTD and placebo), visit, treatment-by-visit interaction, stratification factors, and baseline body weight as a covariate. An unstructured covariance structure will model the relationship of within-patient errors. The Kenward-Roger approximation will be used to estimate the denominator degrees of freedom.

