4.3.2. Main Analytical Approach

4.3.2.1. Analysis Related to the Treatment Regimen Estimand

The analysis related to the treatment regimen estimand will be conducted using the FAS.

The analysis for the mean percent change in body weight will be conducted utilizing ANCOVA. The response variable for the ANCOVA model will be percent change in body weight from randomization to Week 88. This model will include terms of treatment group, country/pooled country, sex, tirzepatide MTD dose at randomization, and body weight at randomization (Week 36) as covariates. The ANCOVA analysis will be conducted with multiple imputation of missing data guided by hybrid method at Week 88 (see Section 4.1 and Section 4.3.2.3 for details) and statistical inference over multiple imputation of missing data guided by Rubin (1987).

With the aid of the ANCOVA model, 2-sided 95% CI for mean percent change in body weight from baseline to the 88-week visit between tirzepatide MTD and placebo will be derived.

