4.3.2.2. Analysis Related to the Efficacy Estimand

The analysis related to the efficacy estimand will be conducted utilizing data in the EAS.

For the mean percent body weight change from randomization, a MMRM will be conducted. Restricted maximum likelihood (REML) will be used to obtain model parameter estimates and

the Kenward-Roger option will be used to estimate the denominator degrees of freedom. The response variable of MMRM will be the percent change in body weight from baseline values obtained at each scheduled postbaseline visit.

For the MMRM model, the independent variables of analysis model are treatment group, visit, treatment-by-visit interaction, and stratification factors (country/pooled country, sex, and tirzepatide MTD dose at randomization) as fixed effects, and body weight at randomization (Week 36) as a covariate. An unstructured covariance structure will model relationship of within-patient errors. If this model fails to converge, the following variance covariance structures will be tested in order until convergence is achieved:

- heterogeneous Toeplitz
- heterogeneous first order autoregressive
- heterogeneous compound symmetry
- Toeplitz
- first order autoregressive, and
- compound symmetry.

The first covariance structure that converges will be used.

With the aid of the MMRM analysis, 2-sided 95% CIs for mean percent change in body weight from randomization to the 88-week visit for tirzepatide MTD compared to placebo will be derived and summarized. The resulting LSM estimates of mean percent change in body weight from baseline will be plotted by visit and by study treatment.

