4.4.2. Key Secondary Efficacy Analyses Subject to Type 1 Error Rate Control

Table GPHN.4.2. Secondary Measures Controlled for Type 1 Error

Objectives	Relative to the efficacy measure:	Analysis conducted in a manner similar to	Additional Information
Tirzepatide MTD QW is superior to placebo:	Mean change in body weight (kg) from randomization (Week 36) to Week 88	For treatment regimen estimand: ANCOVA model described in Section 4.3.2.1. For efficacy estimand: MMRM model described in Section 4.3.2.2.	LSM estimates will be plotted by treatment through 88 weeks.
	Mean change in waist circumference (cm) from randomization (Week 36) to Week 88	For treatment regimen estimand: ANCOVA model with terms of treatment group, stratification factors, and corresponding value at randomization (Week 36) as covariates. For efficacy estimand: MMRM model with treatment group, visit, treatment-by-visit interaction, all stratification factors as fixed effects, and corresponding value at randomization (Week 36) as covariates.	LSM estimates will be plotted by treatment through 88 weeks. Refer to Sections 4.3.2.1 and 4.3.2.2 for analysis approach detail.
	Percentage of participants who maintain $\geq 80\%$ of the body weight lost during the 36 weeks of open-label period	For both treatment regimen and efficacy estimand: Logistic regression model will be conducted.	Refer to Section 4.4.1 for analysis approach detail.
Tirzepatide MTD QW is superior to placebo:	Percentage of study participants who achieve $\geq 5/10/15/20\%$ body weight reduction from Visit 2 (Week 0) to Week 88	For both treatment regimen and efficacy estimand: Logistic regression model will be used.	Refer to Section 4.4.1 for analysis approach detail.
	Time (in weeks), during the 52-week double-blind treatment period, to first occurrence of participants returning to $>95\%$ baseline weight for those who have already lost $\geq 5\%$ since Week 0	For both treatment regimen and efficacy estimand: Cox-proportional hazards model will be used with the terms of treatment group (tirzepatide MTD and placebo), country/pooled country, sex, tirzepatide MTD dose at randomization, and weight at randomization (Week 36) and at baseline (Week 0) as covariates.	Only for participants with at least 5% body weight loss during the open-label lead-in period. For treatment regimen estimand: the participant without event will be censored at Week 88.

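### The efficacy-estimand MMRM gives each covariate one coefficient for all visits, which may forgo some precision at Week 88; covariate-by-visit terms are a cheap improvement.

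*Protocol*

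**What the plan says.** Protocol 9.4.1 sets the general MMRM "with terms of treatment, visit, treatment-by-visit interaction, stratification factors, and baseline measurement as a covariate". Protocol 9.4.3.1 repeats this for the primary endpoint: "The independent variables are treatment group (tirzepatide MTD and placebo), visit, treatment-by-visit interaction, stratification factors, and baseline body weight as a covariate". It adds: "An unstructured covariance structure will model the relationship of within-patient errors". The model's role is limited: "For all other purposes, the primary efficacy analysis will be guided by the “efficacy” estimand".

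SAP 4.3.2.2 keeps one interaction: "the independent variables of analysis model are treatment group, visit, treatment-by-visit interaction, and stratification factors". It enters "stratification factors (country/pooled country, sex, and tirzepatide MTD dose at randomization) as fixed effects, and body weight at randomization (Week 36) as a covariate", so the percent-weight-loss stratum is not in the SAP model.

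Other models follow the pattern. In SAP Table GPHN.4.2 the efficacy-estimand waist analysis is an "MMRM model with treatment group, visit, treatment-by-visit interaction, all stratification factors as fixed effects, and corresponding value at randomization (Week 36) as covariates", and change in kg uses the 4.3.2.2 model. In Table GPHN.4.3 the models for weight, BMI and waist change since Week 0 also have treatment by visit as their only interaction.

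The treatment-regimen analysis differs (SAP 4.3.2.1): "The response variable for the ANCOVA model will be percent change in body weight from randomization to Week 88". It fits one visit, so its covariate coefficients belong to Week 88.

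**The concern.** Week 40 comes 4 weeks after randomization and Week 88 comes 52 weeks after. Change since Week 36 has had little time to develop at Week 40, so its SD and its relation to weight, sex or dose are probably small there and larger later.

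Under an unstructured covariance, a coefficient forced to be equal at all visits is a precision-weighted average of the visit-specific coefficients, and a low-variance visit dominates it. Week 88 would then be adjusted with a coefficient closer to the Week 40 value.

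At stake is the width of the efficacy-estimand confidence interval at Week 88. There is a secondary use: SAP 4.4.1 fills missing responder outcomes for this estimand from MMRM predictions, so the same coefficients enter there.

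**Working it through.** **Inputs from the documents.** Protocol 9.2: 300 per arm, SD 8%, difference 6%, dropout 25% (225 per arm remain), two-sided 0.05. Protocol 1.3 and 4.1.1.2.2: 13 visits after randomization, 8 of them by telephone, leave five weight visits, at Weeks 40, 52, 64, 76 and 88 (t = 4, 16, 28, 40, 52 weeks after randomization).

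**Inputs assumed.** Week 88 covariate R2 of 2%, 5% or 10%; the SD path; the between-visit correlation; the path of the covariate effect. The documents give none of these.

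**Step 1: the plan's own figure.** SE = 8 × √(2/225) = 0.754 and 6/0.754 = 7.95. Power = Φ(7.95 − 1.96) > 0.9999, consistent with the stated figure of more than 90%.

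**Step 2: what the model does.** With complete data and treatment by visit saturated, the Week 88 effect is D(Y88) − b × D(X). D is the difference between arms and b is the common coefficient. b is the weighted mean of the visit-specific coefficients, with weights proportional to S⁻¹1, where S is the residual covariance under the common-coefficient model (iterated to a fixed point). Then:

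- share of the covariate gain lost: L = (b88 − b)² / b88²
- SE ratio, common versus by-visit: √[(1 − R2 + R2 × L) / (1 − R2)]

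**Step 3: one case by hand.** Let change build up in independent steps, so that variance is proportional to t, and let the covariate effect grow linearly. All the weight then falls on Week 40, and b/b88 = 4/52 = 0.077. L = (1 − 0.077)² = 0.85. At R2 10% the ratio is √[(0.90 + 0.085)/0.90] = 1.046.

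**Step 4: the range.** In the table, AR means autoregressive (correlation per 12 weeks) and CS compound symmetry.

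| Assumed pattern | Week 40 weight | L | SE ratio at R2 2% / 5% / 10% |
|---|---|---|---|
| Independent steps, linear effect | 0.99–1.00 | 84–85% | 1.009 / 1.022 / 1.046 |
| Independent steps, square-root effect | 0.96–0.99 | 50–52% | 1.005 / 1.013 / 1.027 |
| CS 0.8, SD as √t, linear effect | 1.31–1.33 | 136–141% | 1.014 / 1.036 / 1.076 |
| AR 0.9, constant SD, linear effect | 0.35–0.42 | 15–20% | 1.002 / 1.005 / 1.008 |
| CS 0.6, constant SD, linear effect | 0.13–0.19 | 14–20% | 1.002 / 1.005 / 1.008 |
| Effect constant over visits | any | 0% | 1.000 |

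A weight above 1 is offset by negative later weights, and L above 100% is worse than no adjustment. Over all growing-SD, growing-effect patterns tried, the Week 40 weight was 0.45 to 1.56 and L was 34 to 141%. With constant SD, L was 3 to 20%.

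**Step 5: simulation with dropout.** An unstructured MMRM with 300 per arm and 25% random dropout, independent steps plus noise and a linear effect, lost 83% of the gain. The SEs were 0.710 against 0.704 at R2 2%, and 0.704 against 0.677 at 10%. Mean estimates were about −6 and the null was rejected in every run under both models.

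**Step 6: absolute scale.** With 225 per arm and no covariate gain, the 95% CI half-width is 1.96 × 0.754 = 1.48 points. With the full gain it is 1.46 (R2 2%), 1.44 (5%) or 1.40 (10%).

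**The case against.** The strongest reply is that the model is valid, serves only one of two analyses, and may lose little. Much of this stands.

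- **Covariate strength is unknown.** The response is already scaled by Week 36 weight and the SAP model omits the weight-loss stratum, so R2 could be nearer 2% than 10%.
- **No decision turns on it.** Power for the 6-point difference stays above 99.99% either way.
- **Scope is narrow.** The treatment-regimen estimand, used for primary disclosure and FDA submission, has its own Week 88 ANCOVA. Two estimands on two data sets need not share a model.

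Three stronger readings are tempting, and the documents do not support them.

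1. A reader might infer that Week 88 is adjusted almost entirely with Week 40 coefficients and that most of the gain is lost. That needs SDs, correlations and an effect path that the documents do not give.
2. A reader might infer that chance imbalance in sex or dose goes uncorrected. Randomization is stratified on both (protocol 6.3, SAP 1.3), which already limits it. Among the covariates in the SAP model, only Week 36 weight is not a stratification factor.
3. A reader might infer bias. Randomization protects the estimate unless dropout depends on the covariates differently by arm. If log-odds of dropout of ±0.3 per SD of the covariate, opposite in sign by arm, are assumed, the two models differ by roughly 0.2 points at R2 5 to 10%. With equal dependence in both arms the gap is at most 0.04. Nothing in the documents points to the opposite-sign pattern.

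The reply does not show that the common coefficient is the better choice. Constant effects sit poorly with a short first interval: with independent steps, Week 40 variance is 64 × 4/52 = 4.9, while a constant effect with R2 10% would alone need 6.4.

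**Conclusion.** The point holds as a modest efficiency improvement. It is certain from the text that each covariate has one coefficient across visits in these MMRMs. It is plausible, but not shown by the documents, that this coefficient leans on Week 40.

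Over the assumed patterns the Week 88 SE is about 0 to 1% larger at R2 2%, 0 to 4% at 5% and 0 to 8% at 10%, and not larger at all if the effects are constant over visits. Only the Week 88 SD of 8% comes from the plan. The superiority conclusion and the treatment-regimen ANCOVA are not affected.

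The calculation applies to change since Week 36. For waist change since Week 0, adjusted only for the Week 0 value among baseline measurements, the Week 40 variance already includes 36 weeks of change. That case is probably closer to the constant-SD rows.

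**What to change.** In protocol 9.4.1 and 9.4.3.1, SAP 4.3.2.2, the efficacy-estimand waist model in Table GPHN.4.2 and the weight, BMI and waist models in Table GPHN.4.3:

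- add the baseline value by visit interaction (both the Week 0 and Week 36 values where a model carries both);
- add sex by visit, and MTD dose by visit where dose is in the model, as far as the model converges;
- leave country as a main effect.

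**Cost.** Five weight visits mean five coefficients in place of one, so four extra parameters per continuous or two-level covariate, small against about 600 participants. Country would cost four per non-reference level, which is why it stays out. Non-convergence becomes slightly more likely. The sequence of simpler covariance structures in SAP 4.3.2.2 already covers this, but the SAP should say that the dose and sex interactions are dropped before the covariance is simplified.
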